Confidentiality will be strictly maintained during each of the research activities. All identifying information will be kept confidential by project staff. Citation and data entry will be made using participant numbers only. All research data will be kept separate from identifiers and linked with participant numbers. Only [name] and her study staff will have access to the file linking names and participant numbers, and this file will be stored in locked cabinets in locked offices at Drexel University for 3 years and then shredded. Electronically collected data (e.g., audio recordings, electronic surveys, databases) will be stored on a research lab computer within an encrypted password protected directory (using Sophos SafeGuard Enterprise) maintained and implemented by Drexel University. All research assistants will be instructed not to discuss research participants outside of the research team. Data will not contain PHI including information pertaining to mental health diagnosis or treatment and is stored on an encrypted backend server (a unique subject identification number will be used in place of participants names to identify input from the app). All statistical analysis will focus on aggregated data, all interview data will be appropriately disguised, and no individual participant will be identified in research reports. Except for release of information required by law, no subject identifiable information will be released without the subject's explicit permission. [name] will monitor the data management process and randomly check data storage and management throughout the course of the study.

27) Provisions to Protect the Privacy Interests of Subjects

This study is designed in order to maximize the privacy interest of research participants. Data will be collected from research participants continuously throughout the study by remote assessment (e.g., pre- and post-intervention period) and through continuous contextual assessment methods (e.g., treatment). Survey responses will remain anonymous, and all data will be de-identified with unique subject identifiers. Identifiable information will only be used for payment and scheduling and will be kept separate from all data. Participant contact information may be stored on Calendly, an online booking system vetted by Drexel's Information Security team. All assessments scheduled via Calendly are synced to the corresponding Drexel employee's Outlook calendar and are only visible to those currently on the research team and the research participant. Research participants are invited to use Calendly for scheduling purposes, however, if research participants do not want to use Calendly, they will be offered alternative scheduling methods (i.e., scheduling via email or phone call). Using Calendly is not required to participate in the research study. If a research participant chooses to schedule an assessment via Calendly, they are instructed to only use their first name and the last initial for assessments (i.e., phone screens and clinical assessments) or their unique participant id number to schedule

PROTOCOL TITLE: Using factorial design to examine efficacies of technology-based augmentations for improving treatment adherence and skills utilization in a self-help CBT program for binge eating.

Protocol Version Date: April 19, 2022

assessments. All questions are worded as to minimize stress and anxiety for research participants. Researcher contact information will be provided and research participants will be encouraged to contact if they have any questions regarding the research process.

Protected health information privacy in self-help CBT program. The research team will generate unique user ID and password that will not include any personal identifiable information (PII) to allow participants to access the self-help CBT program. De-identified data pertaining to eating behavior, (e.g., food consumed, binge eating, context for eating episodes) will be automatically transmitted through end-to-end transmission from the base self-help app to an encrypted backend server. End-to-end transmission of digital data will be encrypted over HTTP using TLS1.2 enforced. Our database server utilizes industry-standard encryption techniques (e.g., secure sockets layer; SSL and Transparent Data Encryption; TDE) to facilitate secure data transfer from subject device to study repository). In order to safeguard these data and participants' privacy, the following steps will be taken: (1) Informed consent will be conducted prior to the study screening procedures. The informed consent procedure will fully and in plain English explain which data are shared, the manner of sharing and the potential risks (e.g., another individual gaining access to their mobile device, theft or loss of their mobile device, interception of transmission); (2) participants will be provided with clear instructions for safeguarding data (e.g., setting a password for entry to the smartphone or laptop, setting an automatic timer to lock the device after a certain number of seconds of non-use, keeping the device on their person at all times); (3) data will regularly be downloaded from the encrypted and secure web server by study staff and subsequently removed from the web server; and 4) self-help app will have its own sandbox environment and no data will be shared outside the app. However, the research team will collect and retain any PHI from the medical records obtained through the HIPAA authorization. Any PHI collected will be stored for 7 years.

Protected health information privacy in treatment conditions when Just-in-time, adaptive interventions (JITAs) are turned ON. In addition to above measures to safeguard participants' data and privacy, in treatment conditions when JITAs are turned ON, following steps will be taken. 1) Intervention messages will only be accessible via smartphone app which will be password protected, 2) Intervention messages will be nondescript and will not include participant's PHI including information pertaining to mental health diagnosis or treatment, and 3) Push notifications will not contain any sensitive information.

28) Compensation for Research-Related Injury

Does not apply. This research does not involve more than minimal risk to subjects.

29) Economic Burden to Subjects

Does not apply. This research will be conducted remotely via Drexel HIPAA-Compliant Zoom software.

30) Consent Process

The Institutional Review Board of Drexel University will have approved the protocol, advertisements, and consent form prior to initiation of the study. Interested parties will be provided with a telephone number and electronic mailing address to contact study personnel for more information regarding the study. A verbal consent form followed by a brief telephone

PROTOCOL TITLE: Using factorial design to examine efficacies of technology-based augmentations for improving treatment adherence and skills utilization in a self-help CBT program for binge eating.

Protocol Version Date: April 19, 2022

screen will be used to assess initial eligibility. If the research participant reports use of compensatory behaviors 3 or more times per week (i.e., purging and/or using laxatives), has a BMI <18.5, or endorses medical symptoms related to their eating disorder on the phone screen, we will ask the research participant to receive medical clearance from his or her PCP prior to enrollment in the study to ensure the research participant is safe to receive outpatient treatment. If the research participant refuses to obtain medical clearance or receive medical monitoring as requested by the study, they will be informed that they will not be eligible for participation in the study. Materials for their PCP will be mailed or emailed to research participants so they can obtain medical clearance for participation prior to their initial clinical assessment visit. If participants meet inclusion criteria based on the screening, the participant will be scheduled for an intake interview and initial assessment via Drexel HIPAA-Compliant Zoom software.. Materials for their PCP will be mailed so that participants can obtain medical clearance for participation prior to their intake interview. Written informed consent will be obtained at the clinical interview. The consent form will contain all pertinent details of the study procedure. Participants will be clearly informed of the voluntary and confidential nature of their participation, and their right to terminate treatment at any given time without penalty. After participants read the consent form, the program staff will paraphrase each segment of the consent form and will answer any questions. If the participant agrees to participate, the consent form will be signed and witnessed. If, during the study period, new study procedures are added (e.g., new assessment measures are added), written consent addendum will be obtained by participants. The consent addendum will allow already enrolled participants to agree to additional study procedures not disclosed in the initial consent form.

Non-English Speaking Subjects

Does Not Apply

Waiver or Alteration of the Consent Process (consent will not be obtained, required information will not be disclosed, or the research involves deception)

Does Not Apply

Subjects who are not yet adults (infants, children, teenagers)

Does Not Apply

Cognitively Impaired Adults

Does Not Apply

Adults Unable to Consent

Does Not Apply

Adults Unable to Consent

PROTOCOL TITLE: Using factorial design to examine efficacies of technology-based augmentations for improving treatment adherence and skills utilization in a self-help CBT program for binge eating.

Protocol Version Date: April 19, 2022
Does Not Apply

31) Process to Document Consent in Writing

Consent will be obtained in writing after an individual has been deemed eligible to participate in the study. After a research participant has read the consent form, they will be asked if they have any questions regarding the research and a member of the research team will be present to read through the consent and answer questions. They will then be asked to sign the consent and initial each page as they review it. Researchers will sign the document as well. They will be given a copy of consent and are encouraged to contact the PI at any time if they have any questions or concerns.

Consent form is attached.

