Patients with frequent or and intense eating disorder pathology, or medical symptoms related to their eating disorder must receive clearance from their primary care physician (PCP) before they can be considered eligible for participation in this study. PCPs will be asked to provide measurements of height, weight, vital signs, and blood draws. PCPs will be notified via letter of their role in determining eligibility for the study and will be provided contact information for the study PI if they have any questions or concerns. Individuals who are or become medically unstable for outpatient treatment will be referred for appropriate medical treatment. Patients must also agree to allow study staff to communicate with their PCP throughout the study and to be reassessed for medical stability if there is a worsening in symptoms. Once a participant is enrolled in the study, study therapists/staff and the PCP will jointly determine the appropriate level of medical care outside of study visits to ensure the participant remains medically stable for outpatient treatment. If patients become medically unstable for outpatient treatment or show a significant and continued worsening in symptoms, they will be removed from the study and referred to a higher level of care. The procedures for medical management of the study patients described above have been successfully utilized by our lab in prior studies of patients with binge eating spectrum disorders. After potential participants are deemed eligible a baseline assessment will be completed. If participants are found to be ineligible at any stage of the process, participants will be given referrals if desired.

Following the baseline assessment, participants will be randomized to receive one of the four treatment conditions and will receive 12 weeks of treatment.

Plans for assessing and/or intervening on suicidal ideation or risk for serious self-harm.

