Coaches will be individuals with bachelor's degree in health-related fields (e.g., psychology, nursing, nutrition etc.) working at the WELL clinic. Coaches are research personnel and have been trained in human subject research through CITI. Coaches will receive training from [name] on reviewing participant's treatment adherence, skills utilization, and self-monitored data and to provide support to participants for improving treatment adherence and skills utilization via emails. Coaches will attend weekly group meetings with [name] to jointly review participants' treatment adherence, skills utilization, and self-monitored data and discuss ways to offer support for improving behaviors related to treatment targets via emails. All assessors will already have had prior training and experience working with individuals with eating disorders. Study personnel will receive specialized training in the administration of assessments. Training will be conducted by [name] will include, but not be limited to, review and discussion of interviews, role playing, and dry runs with practice individuals with live supervision. The project statistician will conduct randomization to prevent the assessor from being a source of bias. The content of the base self- help CBT program will be based on Chris Fairburn's evidence-based Overcoming Binge Eating book.

The standard of care for binge spectrum eating disorder and bulimia nervosa is behavioral treatment. In this project, all the participants will receive self-help CBT program based on [name] evidence based-treatment program for binge spectrum eating disorders and is superior to standard of care. As such, there is no potential of randomizing subjects into a condition that is less than standard of care for their eating disorders.

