Participants will continue in their current medical treatment at time of enrollment. Medical status will be closely monitored throughout the intervention. Participants will be required to sign consent to contact their PCP throughout the study to ensure coordination in care. The PCP will be provided with a letter describing enrollment in the study. Participants will be informed that the research team will inform the PCP if there is a change in symptom status such as notable weight loss, increase in restrictive eating behavior or increase in purging behavior that may require additional medical management. Concurrent psychotherapy for eating pathology will not be permitted during the study as this could confound data. Pharmacological management will be permitted for psychiatric co-morbidities. Any prescribed medications or dosage changes will be carefully tracked through the study.

Assessment Procedure. Assessments will occur at at baseline, mid-treatment, post-treatment, and at 3-month follow-up. In order to maximize assessment completion, we

PROTOCOL TITLE: Using factorial design to examine efficacies of technology-based augmentations for improving treatment adherence and skills utilization in a self-help CBT program for binge eating.

Protocol Version Date: April 19, 2022

will increase compensation across assessments (\$20, \$30, \$50 and \$75). At the beginning of the assessment at the baseline, the assessor will review the IRB approved Consent Form with the prospective participant. Of note, none of the assessments within the proposed study requires prospective participants to provide their signatures except for the Consent Form. Assessments will be conducted by Independent Evaluators (IEs), IEs will be trained until they reach 100% agreement on diagnosis and acceptable reliability (>.80) on EDE scoring. Assessments will be audio recorded for review. Twenty randomly selected tapes will be reviewed to compute reliability statistics. All measures listed below have acceptable psychometric properties.

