Assessments will be conducted by unblinded assessors at baseline, mid-treatment, post-treatment, and at 3-month follow-ups. Assessments will be for a total of 3 hours in length. Assessors for the baseline, mid-treatment, post-treatment, and 3 month follow up will be research coordinators employed and paid by the WELL Center and Ph.D students at Drexel University. Three hours of the assessment is a semi-structured interview in which the participants will be using a zoom link via Drexel's HIPAA compliant Zoom platform the assessor sent prior to the interview to meet with the assessor who conducts the interview with the participant. Total length of participation in this study will be about 7 months from the baseline assessment to the 3-month follow-up assessment. As the study continues, the status of the trial will be updated on <http://www.ClinicalTrials.gov> as different phases of the study start and end (including but not limited to “not yet recruiting”, “recruiting”, “active not recruiting”, and “completed”).

This study will have 2 kinds of blind assessors. One type of blind assessor is the study coordinator. The study coordinator is a full-time paid employee on the study. As part of their job responsibilities, they will conduct assessments for this current study. The other type of assessors is graduate students. Students serve as assessors on clinical trials being conducted in a research lab to receive specialized training and supervision in conducting clinical interviews for assessing eating disorders. Typically, graduate students are obligated to fulfill 8 hours of training time in the specialized research lab without getting paid. Graduate students will be asked to conduct assessments within these 8 hours of free lab time and hence, will not be paid for conducting the assessments. In the conditions with Advanced DDS with Coaches, coaches will be unblinded throughout the 12-week program. Coaches will know the study condition and diagnosis of the specific patients they've been assigned in order to facilitate improvement in treatment targets of the patients they've been assigned. Coaches will be blinded to the clinical outcomes from treatment for the patients they are assigned to. They will be blinded to all clinical outcomes data collected at different assessment time points.

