Blood Draws. As is standard, blood testing to assess for medical complications associated with purging is conducted based on severity of purging behavior. If participants demonstrate purging 3 or more times per week and are deemed unsafe to continue study participation by their PCP, they will be removed from the study to receive medical care of worsened purging behavior, and thus, will not undergo anymore blood testing for the study assessments. If the severity of purging is low (i.e., less than 3

PROTOCOL TITLE: Using factorial design to examine efficacies of technology-based augmentations for improving treatment adherence and skills utilization in a self-help CBT program for binge eating.

Protocol Version Date: April 19, 2022

episodes per week), participants may undergo blood testing once during the study for medical monitoring and to receive PCP clearance to continue study participation in addition to study assessments.

Feasibility and Acceptability. Assessment of feasibility will include number of patients screened per month, % of eligible patients enrolled, treatment attrition (% of patients that prematurely terminate treatment), study retention (% of patients that complete all study assessments), treatment adherence, treatment fidelity. Acceptability will be assessed using the Feedback Questionnaire. During treatment each session will be audio-recorded and 20% of the sessions for each group treatment will be randomly selected for adherence and competency ratings by a blinded IE.

Outcome Measures

Rater-Administered Measures:

- ***Eating Disorder Examination (EDE)***. The EDE is a widely utilized, semi-structured interview for the assessment of eating disorder symptoms. The EDE interview will be audio recorded and will be used to confirm research participant's eligibility. The EDE has been updated to the newest version of this measure.
- ***Mini International Neuropsychiatric Interview (MINI)***. The MINI is a structured psychiatric diagnostic interview.
- ***Body Mass Index (BMI)***. For BMI, height (via stadiometer) and weight (via medical-grade, digital scale) will be assessed in the clinic prior to treatment onset and at each assessment point. This data will be used to calculate BMI. In the case of remote assessments, research participants will weigh themselves at home using digital scales and take their heights using yard sticks or measuring tape.

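### Protocol section 10 calls the same outcome assessors unblinded and then blind, and no other available text says that raters of the post-randomization interviews are masked to condition

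*Protocol*

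**What the plan says.** Two consecutive paragraphs under Assessment Procedure in protocol section 10 describe the assessors.

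- The first says: "Assessments will be conducted by unblinded assessors at baseline, mid-treatment, post-treatment, and at 3-month follow-ups". It then names the staff who do this at all four time points: "research coordinators employed and paid by the WELL Center and Ph.D students at Drexel University".
- The second says: "This study will have 2 kinds of blind assessors. One type of blind assessor is the study coordinator". It explains that the coordinator is a paid employee who carries out this study's assessments, and that the other type of assessor is graduate students working within their lab hours.

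The second paragraph goes on to the coaches: "In the conditions with Advanced DDS with Coaches, coaches will be unblinded throughout the 12-week program". For coaches the protocol says what they know (condition and diagnosis) and what they are kept from (clinical outcomes). For assessors it gives no such detail.

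On timing, section 10 (Screening) says: "Following the baseline assessment, participants will be randomized to receive one of the four treatment conditions".

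**The concern.** The EDE is listed in section 10 as a rater-administered, semi-structured interview, so its scoring involves judgement. The SAP analyses EDE global scores under Primary Aim 3 and plans contrasts on primary outcomes at post-treatment and 3-month follow-up. A participant who receives weekly coach emails can see that this factor is ON, and coaches know the condition of the participants assigned to them. Masking the rater is therefore the main protection left for the interview outcomes, and the protocol both denies and affirms it.

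Staff cannot follow both statements. If they follow the first, interview ratings are open to detection bias. A reader of the results could not tell from the protocol which arrangement applied, and masking cannot be restored once the interviews are done.

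**Working it through.** No arithmetic applies. The check is whether the two statements concern the same people and task, and whether any other text settles the matter.

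**1. Same people, same task.** The labels differ slightly (research coordinator and study coordinator; Ph.D. student and graduate student). The roles are the same, and both paragraphs are about conducting this study's assessments. The two descriptions cannot both hold.

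**2. When it matters.** Randomization follows baseline, so there is no allocation to know at that visit. The mid-treatment, post-treatment and 3-month assessments remain: three of four. The schedule table in section 10, as extracted, shows no 3-month column, but the text of section 10 includes that visit and the SAP power section uses four assessment points for the efficacy outcomes.

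**3. Other text that might settle it.**

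| Place | What it covers | Masks outcome raters to condition? |
|---|---|---|
| Section 10, Ensuring participants receive high-quality interventions: "The project statistician will conduct randomization to prevent the assessor from being a source of bias" | Who randomizes | No; silent on knowledge of allocation afterwards |
| Section 10, Assessment Procedure, and section 22, Independent Evaluator Training | Evaluators called independent, with reliability standards | No; masking is not mentioned |
| Section 22, same paragraph | Participant identity is not to be discussed, to protect ratings | No; identity, not condition |
| Section 10, Feasibility and Acceptability: "randomly selected for adherence and competency ratings by a blinded IE" | Ratings of recorded treatment sessions | No; not the outcome interviews |
| Section 12, Blinding of Data | De-identification of data | No |
| SAP, statistical design and power text | Models, aims, power | No; assessor masking is not mentioned |

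Part of the SAP was not available, so the statement is limited to the text provided.

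**4. A related mismatch.** Section 10 has coordinators and doctoral students conducting assessments. Section 22 describes the evaluators who conduct outcome assessments as doctoral students only.

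**5. Which outcomes are reached.**

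- EDE global (Aim 3): affected, because it comes from the interview.
- Binge-eating frequency (Aim 3): affected if taken from the EDE. Its source is not stated. The app also records binge eating (section 12), although four assessment points fit an interview.
- Aim 4 outcomes: the same condition applies.
- Aim 1 adherence and skills use: not affected, because they come from app data and self-report.

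**The case against.** The strongest reply is that a single word is wrong. The paragraph that calls the assessors blind is the more detailed one. It goes role by role and sets the assessors against coaches who are expressly unblinded. Randomization is kept with the statistician to protect against assessor bias, and the evaluators are called independent. This stands as the more likely reading. It does not dispose of the point, because the conflicting sentence is operative text and only the sponsor can say which statement is true. Nor would deleting two letters be quite enough, since the protocol still would not say what the assessors are blind to.

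A reader might go further in two ways that the documents do not support.

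- *That outcomes will be rated unblinded and the efficacy results biased.* The text leans the other way, and nothing in the documents allows the direction or size of a bias to be worked out.
- *That the plan contains two leaks in the blind.* Section 15 has a coach's report of worsening symptoms passed to the research coordinator, which would show that Advanced DDS with Coaches is ON. The Feedback Questionnaire is an interview about the treatment at mid- and post-treatment. The first unmasks a rater only if an alert occurs and the notified coordinator also rates that participant. The second does so only if the EDE rater conducts it and learns the condition before an EDE is rated. The documents establish none of these conditions. They are reasons for care if blinding is intended, not errors in the plan.

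**Conclusion.** The point holds as an internal contradiction: section 10 describes the same assessors as unblinded and as blind, and no other available text says that raters of the post-randomization interviews are masked to condition. It concerns three of the four assessment points. It certainly reaches EDE global scores. It reaches binge-eating frequency and the Aim 4 outcomes on the assumption that these are taken from the EDE. Aim 1 is untouched. No size of bias is claimed. That blinding is intended is an inference from context and needs the sponsor's confirmation. The text should be corrected because it governs a core control on bias and the correction costs almost nothing.

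**What to change.** **Required.** Reconcile the two paragraphs in section 10.

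- If blinding is intended, replace the word unblinded with a statement that assessors are blinded to condition at the mid-treatment, post-treatment and 3-month assessments. Make sections 10 and 22 agree on whether coordinators rate outcomes.
- If assessors are in fact unblinded, say so plainly and report the interview outcomes as unblinded.

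This costs a few words of text.

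**Optional, if blinding is intended.**

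- Complete the EDE before the Feedback Questionnaire at each visit. This protects the rating at that visit only, not at the next one.
- Where a coordinator has received a coach's alert about a participant, have another existing assessor who is not a coach rate that participant's later EDEs. The notification in section 15 stays as it is.

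These add no interviews. The downside is minor scheduling among existing assessors, whose number the documents do not give. They would not guarantee masking, since a participant may mention coach emails or app messages in any interview.
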